2. Attach electrodes (so they're visible in the baseline video for optimal blinding).
3. Check resistance through electrodes. If $< 100 \Omega$, look for a short and correct it. If resistance remains out of range, do not proceed without specific approval from PI. Record resistance.
4. Optional but recommended bathroom stop
5. Procedures below are performed in a quiet room with only participant and study staff present but not conversing
6. All videos are recorded from the elbows up for later blinded ratings of tics
7. 5-min video-recorded baseline session, also rated live at the first visit to record baseline tic

frequency

8. At this point, the PI or designate will review the inclusion and exclusion criteria (including mean baseline tic frequency $\geq 1/\text{min.}$) and document eligibility for the study before additional procedures
9. Determine stimulation threshold for a train of 8 pulses (12 Hz, pulse width 200 μs), starting at 1mA and increasing until a twitch of the thumb is seen, to a maximum of 20mA (expected range 2-15 mA, *personal communication, [name] to [name]*). Some subjects may wish to withdraw at this point if suprathreshold stimulation is too uncomfortable, but in the Nottingham report, participants age 15 and up found the stimulation tolerable. Since electrode placement can change slightly between visits, on the second visit the threshold is verified and adjusted as needed. We record the threshold at each visit.
10. Resume video recording
11. Synchronize clocks for video, urge rating software, and stimulation
12. MNS stimulation on or off blocks as follows, without planned breaks (total 29-44 min.)
 - a. Two 1-min. blocks of MNS on and two 1-min. sessions off, the order of these 4 sessions randomized (*this design matches the Nottingham study*)
 - b. 5-min. block MNS off
 - c. 5-min. block MNS on
 - d. 5-min. block MNS off
 - e. 5-min. block MNS on
 - f. 5-minute stimulation **off** blocks until tics return to baseline frequency (min. 1 block, max. 4 blocks)
13. Stop video recording
14. CGI-I (Clinical Global Impression of Improvement) rating for tics by participant and investigator
15. Debrief
 - a. ratings of tic improvement and discomfort using the CGI Efficacy Index
 - b. ask for comments on benefit, tolerability, side effects
 - c. participant and staff guess whether this was active or control stimulation day (*to test adequacy of blinding*)
 - d. ask if they think they would use a portable stimulator

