From these data, a sample size of 32 will have 81% power to find a statistically significant result for Aim 1 (two tails) assuming the population mean response is the 30% reported by our colleagues in Nottingham. This sample size provides 75% power to detect clinically meaningful (-25%) improvement (one tailed).

Estimating screen failures and dropouts at a total rate of 27%, we will plan to enroll up to 44 participants to arrive at 32 who complete the entire study.

INCLUSION CRITERIA

Inclusion criteria for all subjects:

- Age 15-64 inclusive at initial screening visit
- Informed consent by adult subject; assent by child and informed consent by guardian
- Current DSM-5 Tourette's Disorder or Persistent (Chronic) Tic Disorder
- At least 1 tic per minute (average) during the first 5-min. baseline video session on the first visit (as scored during the session by the investigator)

EXCLUSION CRITERIA

Exclusion criteria for all subjects:

- Unable to complete study procedures for any reason
- Has an implanted device that could be affected by electrical current
- Pregnancy known to participant or (for children) to the parent
- Known or suspected primary genetic syndrome (e.g. Down syndrome, Fragile X)
- Intellectual disability (known, or likely from history and examination)
- Head trauma with loss of consciousness for more than 5 minutes
- Significant neurologic disease, not counting TS (exceptions include febrile seizures or uncomplicated migraine)
- Severe or unstable systemic illness
- Factors (such as exaggerated signs) that in the judgment of the principal investigator make the video recording or YGTSS an inaccurate assessment of tic severity
- Judged by investigator to be unlikely to complete study procedures or to return for later visits
- Change in somatic or psychotherapeutic treatment in the 2 weeks preceding the first stimulation visit
- Planned change in somatic or psychotherapeutic treatment between the 2 stimulation visits

CONCOMITANT MEDICATIONS

Required: none

PROHIBITED MEDICATIONS

none

TREATMENTS AND DOSAGE

Rhythmic

- 10 Hz for 1-minute epochs (to replicate **Current Biology** report)

- 12 Hz for 5-minute epochs

Arrhythmic

- Same number of pulses per minute as in the rhythmic condition, but with a random inter-pulse interval, as implemented by the Nottingham group in the **Current Biology** report

Both

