- Square-wave 200 μ s pulses triggered by computer at the threshold for thumb movement (expected ~2-15mA) to surface electrodes over the median nerve at the right wrist (conductive gel, 30 mm apart center-to-center, anode distal)

ANALYSIS PLAN/APPROACH/METHODOLOGY

Outcome measures

The primary outcome measures are derived from audiovisual recordings (head to elbows), later broken into 1-min. or 5-min. clips, then rated in random order by an experienced movement disorders physician blind to stimulation conditions (on vs. off, rhythmic vs. arrhythmic) and order (rhythmic at first or second visit), who will record tic frequency and rate severity. For the 1-min. MNS on/off blocks, severity is rated on a 5-point scale (from the YGTSS severity item) for each occurrence of any tic, to replicate the methods of the Nottingham group. For the 5-min. blocks, overall tic severity is rated on the same scale once for each 5-min. block. This choice dramatically reduces rater time without sacrificing validity. Analysis for each participant can begin after his/her second stimulation visit is complete and all other data from that participant is checked.

Primary Outcome Measures:

1. Change in tic frequency compared to when MNS is off

An expert rater blind to condition and time point assesses the number of tics per minute. A one-tailed t test will compare mean tic frequency in the last 40 s of on vs. off 1-minute stimulation epochs on the rhythmic MNS day. This analysis replicates that of Study 3 in the Morera Maiquez et al 2020 citation. A secondary analysis will test for carryover effects.

[Time Frame: During rhythmic MNS stimulation]

2. Change in tic severity compared to when MNS is off

Severity is rated on a 5-point scale for each occurrence of any tic. The scale is the Intensity item from the Yale Global Tic Severity Scale [YGTSS], which uses integer scores from 0 (no tics) to 5 (severe intensity). A one-tailed t test will compare mean tic severity in the last 40 s of on vs. off 1-minute stimulation epochs on the rhythmic MNS day. This analysis replicates that of Study 3 in the Morera Maiquez et al 2020 citation. A secondary analysis will test for carryover effects.

[Time Frame: During rhythmic MNS stimulation]

3. Change in tic frequency during rhythmic MNS (vs. arrhythmic MNS)

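### The 1 tic/min inclusion criterion is counted live with no in-frame condition, while all four primary outcomes are rated from head-to-elbows recordings

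*Combined protocol and SAP*

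**What the plan says.** **Eligibility count.** The Inclusion Criteria ask for "At least 1 tic per minute (average) during the first 5-min. baseline video session on the first visit (as scored during the session by the" …, and name the investigator as the scorer. In the Stimulation protocol, step 7 is a "5-min video-recorded baseline session, also rated live at the first visit to record baseline tic" frequency. At step 8, straight after that session, the PI or a designate "will review the inclusion and exclusion criteria" and documents eligibility. No body region, tic type or camera view is specified for the count, and no step compares it with the recording.

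**Outcome source.** Step 6 says "All videos are recorded from the elbows up for later blinded ratings of tics". Under Outcome measures, "The primary outcome measures are derived from audiovisual recordings (head to elbows"), and all four primary outcomes are blinded ratings of those clips.

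**Related text.**
- Step 2 has the electrodes, which sit at the right wrist, attached before baseline so that they show in the baseline video.
- The Exclusion Criteria let the principal investigator exclude for factors that "make the video recording or YGTSS an inaccurate assessment of tic severity". The one example given is exaggerated signs.
- The recordings carry sound, and phonic intensity enters the severity score for the 5-minute blocks (primary outcome 4).

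**The concern.** The screening count and the outcome are not the same quantity. An investigator in the room can see the whole participant; the blinded rater sees head to elbows and hears the audio. Someone whose baseline tics are mostly in the legs or feet can pass at 1 tic/min or more and then supply few scorable tics in either the on or the off blocks.

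Such a participant counts as one of the 32 completers but can show almost no on/off difference in frequency. Primary outcome 2 rates severity for each tic occurrence, so it too has little or nothing to rate. The study is meant to yield a go/no-go signal for a later trial, and its stated power (81% and 75%) leaves little room for avoidable dilution.

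**Working it through.** **1. The plan's own figures.** From Power considerations: mean on/off difference about 41, SD of the difference about 81 (total tics per condition), N = 32. Alpha = 0.05 is assumed for Aim 1.

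- Standardised difference: 41/81 = 0.506. Paired t test (noncentral t), two-sided: 79.2%; normal approximation 81.7%. Stated: 81%.
- 25% decrease: 41 × 25/30 = 34.2; 34.2/81 = 0.422. One-sided power 75.4%. Stated: 75%.
- Enrolment: 32/(1 − 0.27) = 43.8, so 44. Stated: 44.

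All three reproduce, so no error in the sample size is alleged.

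**2. One person exactly at threshold, Aim 1.** Two off blocks with the last 40 s of each scored give 80 s per condition. With a fraction q of tics in frame, expected scored tics = (80/60) × 1 × q. Under a Poisson assumption the chance of none is exp(−mean).

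| Share in frame (assumed) | Expected tics, off condition | Chance of none |
|---|---|---|
| 100% | 1.33 | 26% |
| 50% | 0.67 | 51% |
| 25% | 0.33 | 72% |

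The 26% in the first row comes from the low threshold and short window, not from framing. Framing accounts for the rise above it.

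**3. The same person, Aim 2.** The first six 5-minute blocks are baseline, 12b, 12c, 12d, 12e and the first 12f block. Four are off (20 min) and two are on. Expected off-condition tics = 20 × q.

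| Share in frame (assumed) | Expected tics, off condition | Chance of none |
|---|---|---|
| 50% | 10 | exp(−10), about 0.005% |
| 25% | 5 | exp(−5), about 0.7% |

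The near-empty counts are therefore an Aim 1 problem.

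**4. Trial-level sensitivity, Aim 1.** Assume a fraction f of completers has no in-frame tics (difference 0) and the rest follow mean 41, SD 81.

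- Mixture mean = (1 − f) × 41
- Mixture variance = (1 − f) × 81² + f(1 − f) × 41²
- At f = 0.10: mean 36.9; variance 5904.9 + 151.3 = 6056.2, so SD 77.8; ratio 0.474
- At f = 0.20: mean 32.8; variance 5248.8 + 269.0 = 5517.8, so SD 74.3; ratio 0.442

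| f (assumed) | Completers affected | Two-sided, 30% effect | One-sided, 30% effect | One-sided, 25% effect |
|---|---|---|---|---|
| 0 | 0 | 79.2% | 87.6% | 75.4% |
| 5% | 1.6 | 76.6% | 85.7% | 73.2% |
| 10% | 3.2 | 73.8% | 83.6% | 70.9% |
| 20% | 6.4 | 67.7% | 78.8% | 65.8% |
| 30% | 9.6 | 60.9% | 73.0% | 60.2% |

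The one-sided columns are shown because the Aim 1 test itself is specified as one-tailed. The 25% column uses 34.2 in place of 41 in both formulas.

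**The case against.** **A safeguard exists.** The exclusion for an inaccurate video recording is worded non-exhaustively, and tics mostly out of frame would fit it. It is reviewed at step 8, before any stimulation. This stands in part: it could remove some such people, but it is a matter of judgement, its only example points elsewhere, and it sets no in-frame minimum.

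**The criterion may already mean in-frame tics.** It is tied to the baseline video session, so an investigator might count only what the camera sees. The text allows that reading but does not state it, and the parenthesis points to live scoring.

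**The frame is uncertain.** A reader might infer that hand and finger tics are lost. The documents do not settle this: step 2 expects the wrist electrodes to be visible, which sits badly with elbows-up framing. Only leg and foot tics are clearly outside on either reading.

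**Not every tic outcome is affected.** The CGI-I ratings and the CGI Efficacy Index are not scored from video, and audible phonic tics are captured. The point is confined to motor tics in outcomes rated from the recordings.

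**The size is unknown.** The documents give no share of affected participants, and the threshold case with 50% or 75% out of frame is an illustration. The sensitivity also assumes that the planning mean and SD describe people whose tics are captured. If the earlier study's sample already included similar participants under similar framing, some dilution is already in those figures and the loss shown is too large. All of this stands.

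**Conclusion.** The gap is real but bounded. As written, the criterion can admit people whose qualifying motor tics the blinded rater cannot see, and the discretionary exclusion closes this only in part.

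The consequence falls mainly on Aim 1, where 80 s per condition leaves little to score. Under the mixture assumption, two-sided power falls by about 5 points if 10% of completers have no in-frame tics (79% to 74%) and by about 12 points at 20% (79% to 68%). These are sensitivity values; the true share is not in the documents.

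Two stronger inferences are not supported. One is that Aim 2 is near the floor: with 20 off minutes, a threshold participant with three quarters of tics out of frame still has 5 expected scored tics. The other is that the comparison is biased: each participant is their own control and the framing rule is the same in every block, so the effect is dilution and lost power.

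**What to change.** In the inclusion criterion and in step 8, state that the count of at least 1 tic per minute includes only motor tics visible within the recorded frame and audible phonic tics, and have the investigator score against the camera view. Confirming the threshold on the baseline recording before eligibility is documented would serve as well.

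Reconcile the elbows-up framing in step 6 and Outcome measures with the statement in step 2 that the electrodes are visible in the baseline video, so that it is clear whether the hands are in frame.

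The cost is a sentence in each place. Outcomes and analysis do not change. There may be some extra screen failures, to be absorbed within the combined 27% allowance and the ceiling of 44; the documents do not allow their number to be estimated. People whose tics are mostly out of frame would not be studied, though the video-rated outcomes could say little about them in any case.

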You may experience one or more of the risks indicated below from being in this study. In addition to these, there may be other unknown risks, or risks that we did not anticipate, associated with being in this study. You will be told of any new information that may affect your willingness to participate in this study. [name] will answer any questions you have about these risks.

MNS

Likely:

- Discomfort in the forearm, wrist or hand during active stimulation
- Mild skin irritation from applying or removing the surface electrodes

Other study procedures

Likely:

- The questionnaires and interview may be slightly boring, fatiguing or challenging.
- The video recordings may be slightly boring

Rare:

- The questions that you are asked during this study could make you feel uncomfortable. If any question makes you feel uncomfortable, you may choose not to answer it.
- Confidential information about you may be accidentally disclosed. However, we think the risk of accidental disclosure is small. The information we gather during the course of the study is coded only by a study number and is kept separately from your name, address, etc.

LOCATIONS / SITES OF STUDY

Data collection: Washington University in St. Louis

Data analysis: Washington University in St. Louis

STUDY DURATION

Anticipated duration of entire research activity per participant:

- 2-4* days, usually over the course of 1-2 weeks

* Planned participation includes a screening visit followed by two stimulation sessions, the first of which may occur on the same day as the first stimulation session. The maximum of 4 days rather than 3 allows one additional make-up MNS session for each participant in the event of technical problems that prevent completion of the procedures.

Anticipated duration of entire research activity:

One year

SAMPLE SIZE

N = 32 (study completers)

Power considerations

We can estimate variance from the Nottingham tic frequency results. Fig. 5 in ref. [6] shows the SD of the improvement in tic frequency between the MNS on and off conditions to be ~81 (total tics per condition). The mean difference between conditions was ~41, corresponding to a nearly 30% mean decrease in tic frequency. A 25% decrease in tic severity using the YGTSS Total Tic Score (TTS) is highly predictive of *clinically meaningful* clinical improvement [17], and the TTS is highly correlated to tic frequency on video recordings [18,19].

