[Time Frame: 5-25 minutes after the end of stimulation at each study visit up to 1 month]

12. Interest in a portable stimulator

Participants answer the question, "If you had a portable device (about the size of a deck of cards) that delivered stimulation in your daily life like you received either today or at your previous visit, would you expect to use it?"

[Time Frame: Once at the end of the second study visit]

Data analysis

Data storage, sharing and management. Phenotypic data will be collected and stored on REDCap (redcap.wustl.edu). This data will not contain PHI and will be shared on the [Open Science Framework](#). Video recordings will be shared only with explicit optional informed consent.

Overall statistical approach. To prevent "HARKing" (hypothesizing after results are known) [20], we have **registered our hypotheses** and analysis strategy on [OSF.io](#) prior to initiating enrollment. For this pilot study, all statistical tests will be reported independently. Aim 1 and Aim 2 test a small number of hypotheses, and Aim 3 results, which are primarily hypothesis-generating, will be presented with a warning about multiplicity of tests.

Aim 1 (replicating the Nottingham results). The analysis will replicate that of Study 3 in the **Current Biology** report [6], with blinded ratings of tic frequency and severity based on the last 40 s of each 60-s MNS on or off block. A one-tailed t test will compare mean tic frequency in on *vs.* off 1-minute stimulation epochs on the rhythmic MNS day. The analysis will be repeated for tic severity.

Aim 2 (testing whether benefit from rhythmic stimulation exceeds that from the active control, arrhythmic stimulation). Change in tic frequency and severity from baseline are compared between MNS-on epochs on rhythmic *vs.* arrhythmic days. Subjects who do not complete both stimulation visits will not be included in this analysis. A repeated measures ANOVA will be used to compare effects of visit, order (rhythmic day first or second) and stimulation (on *vs.* off) on tic frequency and

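### The plan does not say that the unanalysed first 20 s of each 1-minute clip are withheld from the blinded rater of primary outcomes 1 and 2

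*Combined protocol and SAP*

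**What the plan says.** All places are in the combined protocol and SAP.

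- **What the rater receives.** Outcome measures says the recordings are audiovisual, framed from head to elbows, and "later broken into 1-min. or 5-min. clips, then rated in random order by an experienced movement disorders physician blind to stimulation conditions". Video analysis has the rater mark every tic and, in the 1-minute blocks, grade each one.
- **What is analysed.** For primary outcome 1: "A one-tailed t test will compare mean tic frequency in the last 40 s of on vs. off 1-minute stimulation epochs". For primary outcome 2: "A one-tailed t test will compare mean tic severity in the last 40 s of on vs. off 1-minute stimulation epochs". The Aim 1 paragraph of Data analysis describes the analysis as one "with blinded ratings of tic frequency and severity based on the last 40 s of each 60-s MNS on or off block".
- **How the blocks run.** Step 12 of the Stimulation protocol reads "MNS stimulation on or off blocks as follows, without planned breaks", and its first item is "Two 1-min. blocks of MNS on and two 1-min. sessions off, the order of these 4 sessions randomized". Step 11 synchronises the video and stimulation clocks.
- **What could give the condition away.** The current is set at the threshold for thumb movement. Potential risks lists as likely: "Discomfort in the forearm, wrist or hand during active stimulation".
- **What protects the blind.** The frame stops at the elbows, electrodes are attached before the baseline video, and clips are rated in random order.
- **What checks the blind.** Participants and staff guess whether the day was active or control. No on/off guess by the video rater is described.

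**The concern.** Aim 1 compares on with off blocks within a single session. A participant stimulated at motor threshold can presumably feel which blocks are on, so the rater's blindness is the main protection against measurement bias.

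If the rater watches the full minute, the clip may open on the moment the stimulator starts or stops. A glance at the arm, a flinch, a change of posture or a remark could be seen or heard even with the hand out of frame. The rater would then score the next 40 s with an idea of the condition. Under-counting or under-grading in clips recognised as on would favour stimulation in both Aim 1 primary outcomes, and the tests are one-tailed in that direction. The planned blinding checks would not detect this. The exposure also serves no purpose in the two primary tests, which discard those 20 s.

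**Working it through.** **1. The plan's own figure for Aim 1.** Power considerations gives a mean on-off difference of about 41 tics, an SD of about 81, N = 32 and 81% power (two-tailed). The standard error is 81/√32 = 14.32.

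- Normal approximation: Φ(41/14.32 − 1.96) = Φ(0.90) = 81.7%.
- Noncentral t, 31 df: 79.2%.

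The stated 81% is reproduced to within 2 points. Trimming clips before rating changes none of these inputs.

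**2. Share of the clip that the primary tests discard.** (60 − 40)/60 = 20/60 = 33%.

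**3. How often a clip would open at a switch.** Assumptions: each clip coincides with its block; the six orders of two on and two off blocks are equally likely; a first block that is on counts as a switch-on, and a first block that is off counts as no switch.

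| Order | On-clips opening at a switch-on | Off-clips opening at a switch-off |
|---|---|---|
| on, on, off, off | 1 of 2 | 1 of 2 |
| on, off, on, off | 2 of 2 | 2 of 2 |
| on, off, off, on | 2 of 2 | 1 of 2 |
| off, on, on, off | 1 of 2 | 1 of 2 |
| off, on, off, on | 2 of 2 | 1 of 2 |
| off, off, on, on | 1 of 2 | 0 of 2 |
| Total | 9 of 12 (75%) | 6 of 12 (50%) |

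**4. Do the documents settle whether the rater sees those 20 s?** Two passages have to be set side by side.

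- Outcome measures sends 1-minute clips to the rater. With clocks synchronised and no planned gaps, the natural cut is at the block boundaries, because any other 1-minute cut would mix on and off time. This is an inference; no sentence states it.
- The Aim 1 paragraph ties the ratings to the last 40 s. It can mean that only those seconds are rated, or that the full minute is rated and the data restricted afterwards.

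Neither passage says that the first 20 s are removed or hidden.

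**5. Illustration of the stakes.** The size of any rater bias is purely an assumption. Take no true effect, an off mean of 41/0.30 ≈ 137 tics, SD 81, N = 32 and one-tailed α = 0.05 (0.05 is stated for Aim 2 and assumed for Aim 1). An average under-count of fraction f over all on-clips gives a noncentrality of f × 137/14.32 and these type I error rates for outcome 1 (noncentral t, 31 df):

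| Assumed average under-count | Tics | Type I error |
|---|---|---|
| 0% | 0 | 5.0% |
| 2% | 2.7 | 7.2% |
| 5% | 6.8 | 11.9% |
| 10% | 13.7 | 23.8% |
| 15% | 20.5 | 40.3% |

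The lower rows need substantial bias. If only on-clips that open at a switch can be recognised, and all of them are, an average of 10% requires 10/0.75 = 13.3% of tics to be missed in those clips.

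**The case against.** The strongest reply is that the problem may not exist. The Aim 1 sentence "with blinded ratings of tic frequency and severity based on the last 40 s of each 60-s MNS on or off block" can be read as confining the rating itself to those seconds, and no sentence says that a clip opens at a switch. That reading is available, so the point is an unstated step and not a proven exposure. It does not close the gap, because the other passages point to full 1-minute clips and the two readings call for different video preparation.

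A reader might infer that every on-clip opens with a reaction to onset. The block order rules that out: 3 of 12 on-clips follow another on-block, and half of the off-clips open at a switch-off, so a reaction at the start does not cleanly mean on.

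A reader might also infer that the first 20 s are the most revealing part. The documents do not show this. The discomfort risk covers the whole of stimulation, Safety monitoring expects at most mild and transient discomfort, and participants have already felt the pulses during threshold setting. The elbows-up frame guards against the thumb-twitch cue. Cues that persist through the last 40 s would survive trimming.

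Two practical objections also stand. The carryover analyses of outcomes 1 and 2, and the optional decay fit after each stimulation block, have no stated window and may need the first 20 s, so those seconds should not simply be thrown away. Aim 1 also sets out to match the cited study's methods, and how that study showed its clips to raters cannot be checked from these documents.

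**Conclusion.** The point holds as an unprotected step in the on/off blinding of two of the four primary outcomes. The plan sends 1-minute clips to the rater, analyses 40 s of them, and does not say that the other 20 s are withheld. On the assumption that clips match blocks, 75% of on-clips and 50% of off-clips would open at a switch.

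A reader might go further and conclude that the rater is unblinded, or that the Aim 1 result is biased by a known amount. The documents support neither. Whether a reaction can be seen or heard is a reasonable supposition only, and the type I error rates above follow from assumed under-counts. They show that a modest rater bias would matter, not that one is present. The case for acting is that the safeguard is cheap and costs the primary tests nothing.

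**What to change.** State in Video analysis and Outcome measures that the 1-minute clips are cut to seconds 21-60 before they are loaded for rating. Use the same trimmed clips for primary outcomes 1 and 2 and for the secondary Aim 2 analysis of the 1-minute blocks, which uses the same 40 s. If this is already the intended practice, one sentence saying so is enough.

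State the time window for the carryover and decay analyses. If they need seconds 1-20, rate those as separate clips, in random order, after the primary ratings are locked.

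Optionally, have the rater record an on/off guess for each clip after scoring it. Such guesses need careful reading, since a real fall in tics would itself prompt a guess of on.

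The cost is a change to the video cutting and a sentence or two of text, plus a small extra rating pass if the first 20 s are needed. Clip presentation may also differ from the cited study. The replicated 40-s window, N = 32 and power are unaffected.
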